9.3 SPECIFIC PROCEDURES

It is important to note that children and adolescents will not be enrolled in the current study unless data from adult patients treated with SAR421869 demonstrate that the risk is justified by an anticipated benefit to the patients.

9.3.1 Screening/Baseline Procedures

A screening log must be maintained for all patients screened for entry to the study with reasons for screen failure/not entering the study documented.

Patient screening will take place in the 28 days prior to SAR421869 administration.

During screening, height, weight, sex, reproductive status, inclusion/exclusion criteria, clinical symptoms of Usher syndrome Type 1B, medical history, treatment history, ECG, chest X-ray and anesthesia assessment (as appropriate) will be recorded.

Details of the screening procedures are detailed in the study schedule in [Section 2](#).

9.3.2 Screening Clinical and Laboratory/Diagnostic Measurements

SKP (study part A) or full-field GATE Static Perimetry (study Parts B&C) data from Day -28 will be reviewed by a centralized independent assessor to evaluate patient study eligibility, with regards to the visual field of the worse seeing-eye. If in the assessor's opinion the Day -28 results are borderline in regards to the patients eligibility status then the test may be repeated, the retest will be conducted prior to Day -1.

A pan-retinal photomontage retinal photographic image will be taken at screening to document the whole retina prior to the beginning of the study.

Details of the screening procedures are detailed in the study schedule in [Section 2](#).

Following the completion of SAR421869 administration to the first three patients in the trial (Cohort 1, dose level 1) the fourth patient (Cohort 2, dose level 2) may commence screening prior to a decision being reached by the investigator, the Sponsor and independent data monitoring committee to increase the dose of SAR421869. Similarly, screening by anticipation may be initiated for all subsequent cohorts.

9.3.3 Screening Clinical and Laboratory/Diagnostic Measurements Day -28

The following assessments are required 28 (visit window +10 days) days prior to administration of SAR421869.

- Entry criteria.
- Informed consent/assent.
- Medical history.
- Anesthesia assessment.
- Height.
- Weight.
- Vital signs.
- ECG (not unless clinically indicated in <18 years old).
- Chest X-ray (not unless clinically indicated in <18 years old).
- Physical examination.
- Ophthalmological examination:
 - BCVA (procedure to be performed up to three times in total at screening, once at this visit),
 - Contrast sensitivity,
 - Slit-lamp examination,
 - Intraocular pressure (IOP),
 - Fundoscopy,
 - Autofluorescence,
 - ERG (multifocal and full field),
 - OCT including an infra-red imaging montage,

- Semi-automated Kinetic Perimetry (SKP) full-field German Adaptive Thresholding Estimation (GATE) Static Perimetry and Microperimetry (procedures to be performed up to three times in total during screening, at least once at this visit),
- Fundus photography – including a photomontage.
- Clinical laboratory samples.
- Urinalysis.
- Pregnancy test (not unless clinically indicated in <18 years old).
- Blood for PCR.
- Urine for PCR.
- Adverse events.
- Concomitant medications.

9.3.4 Baseline Clinical Laboratory/Diagnostic Measurements Day -1

The following assessments must either be completed on Day -1 or in the preceding 7 days with the exception of the urine pregnancy test that must be negative on Day -1 (not unless clinically indicated in <18 years old).

- Vital signs.
- Ophthalmological examination:
 - BCVA (procedure to be performed up to three times at screening, twice at this visit),
 - Contrast sensitivity,
 - Slit-lamp examination,
 - Intraocular pressure (IOP),
 - Fundoscopy,
 - OCT including an infra-red imaging montage,
 - SKP, full-field GATE static perimetry and microperimetry (procedures to be performed at least twice and up to three times during screening),
 - VFQ25 questionnaire / CVAQC (when possible).
- Clinical laboratory samples (not unless clinically indicated in <18 years old).
- Urinalysis (not unless clinically indicated in <18 years old).
- Pregnancy test (not unless clinically indicated in <18 years old).
- Blood for immunology.
- Adverse events.
- Concomitant medications.

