- g Liver function: alanine aminotransferase (ALT), aspartate aminotransferase (AST), total bilirubin (TBIL), alkaline phosphatase (ALP), total protein (TP), albumin, gamma glutamic transpeptidase (γGT, GGT), cholesterol (CHOL) (only at screening).
- h Coagulation: prothrombin time (PT), partial thromboplastin time (PTT) at screening and baseline only.
- i Urinalysis: Microscopic urinalysis for protein, blood, ketones.
- j Blood and where possible urine sample 60 minutes after surgery.
- k Week 48 or early termination procedures.
- l Visit window does not apply to urine pregnancy test; must be negative on Day -1.
- m Semi-automated Kinetic Perimetry conducted at screening visits Day -28 may be repeated prior to Day -1 if requested by the centralized independent assessor.
- n Semi-automated Kinetic Perimetry will be conducted twice at baseline (Day -1).
- o In subjects of <18 years only investigations may be omitted unless considered clinically indicated.
- p Infra-red fundus montage to be performed at each visit.
- q Only in patients with a positive antibody response at Week 24

* - VFQ-25 for adults ≥18 years/CVAQC for children <18 years.

**- To be repeated just in case of re-screening, if previous screening was earlier, than 38 days before surgery.

***- anesthesia assessment and physical examination will be repeated if outside 28 days or Day -1 window. Weight, ECG, chest X-ray and additional physical examination may be repeated by request of anesthesiologist at rescreening.

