8.2 ENTRY CRITERIA

Main Inclusion Criteria

For the purposes of this study 1 month is equivalent to 28 days.

Patients must meet ALL of the following criteria to be considered for enrolment into this study.

1. Signed and dated written informed consent must be obtained from the patient (or assent in the case of minors from their legal guardian/representative), in accordance with the local regulations.
2. Clinical and molecular diagnosis of Retinitis Pigmentosa associated with Usher syndrome Type 1B, caused by at least one pathogenic MYO7A mutation on both alleles, confirmed by direct sequencing and co-segregation analysis within the patient's family.
3. Patients must have suitable verbal/auditory and/or tactile sign language communication (in the opinion of the investigator) as to allow written informed consent to be obtained.
4. Females of childbearing potential must have a negative pregnancy test at screening and at baseline, and agree to use an effective form of contraception such as the contraceptive pill or intra uterine device for at least three months following SAR421869 administration, or be surgically sterile or postmenopausal, with the last menstrual period being over two years prior to enrolment.

5. Males of reproductive potential must agree with their partner to use two forms of contraception, including one barrier method for at least three months following SAR421869 administration if their partner is of childbearing capacity, or must be surgically sterile.
6. Patients enrolled in France must be affiliated to or benefit from a social security regimen.
7. Patients must agree to not donate blood, organs, tissues or cells for at least three months following SAR421869 administration.

Part A

Specific Inclusion Criteria Cohorts 1, 2 and 3a

- ≥ 18 years of age.
- Concentric constriction of kinetic visual field centrally in the worse seeing-eye equating to a horizontal visual field diameter of ≤ 20 degrees, measured through the center of the visual field grid. The visual field constriction will be measured by Semi-automated Kinetic Perimetry (SKP) and the degrees of constriction will be confirmed by centralized independent assessment of the SKP data.
- No detectable rod-derived amplitudes on the full field electroretinogram performed to ISCEV standards.

Specific Inclusion Criteria Cohort 3 subgroups 3b and 3c

- ≥ 18 years of age.

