9.2.8 Study Conduct Specific to Children and Adolescents

It is important to note that children and adolescents will not be enrolled in the current study unless data from adult patients treated with SAR421869 demonstrate that the risk is justified by an anticipated benefit to the patients.

The process of informed assent of children/ adolescents and the consent of their parents, guardians or other legal representatives will ensure that all parties understand the unique risks associated with gene therapy as well as the specific risks associated with ocular gene therapy. Moreover, the process will ensure that all parties understand the risks of participating in early clinical research where the safety and efficacy of a therapy may not have been fully established. The management of children and adolescents will be approached on an individual patient basis within the constraints of the protocol and the necessary procedures and monitoring to ensure safety. The patient and parents/legal guardians will be fully informed and consulted at all stages of the research and concerning all decisions regarding the management of the individual during subsequent follow-up.

Signed and dated written informed consent must be obtained from the patient (or assent in the case of minors from their legal guardian/representative), in accordance with the local regulations.

As in adults, the following procedures will be followed when including children and adolescents in the protocol:

- To ensure effective monitoring of both vector and product, biodistribution and immunology samples will be collected at the same intervals as in adult patients.
- Children and adolescents will enter the open label long-term follow-up protocol designed to monitor the long-term safety of patients treated with SAR421869.

Appropriate measures will be implemented to minimize any pain or discomfort associated with study procedures in children, including administering SAR421869 under general anesthesia if necessary, and where appropriate providing in-patient hospitalization for postoperative management.

- The administration of SAR421869 to children of less than 12 years will be under general anesthesia with neuromuscular paralysis and controlled ventilation.
- Postoperative nausea and vomiting will be managed proactively through prophylactic use of anti-emetics.

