9.3.7.1 Follow-up Day 1 Clinical and Laboratory/Diagnostic Measurements

- Vital signs
- Ophthalmological examination:
 - BCVA,
 - Slit-lamp examination,
 - Intraocular pressure (IOP),
 - Fundoscopy,
 - OCT including an infra-red imaging montage,
 - Fundus photography.

- Clinical laboratory samples (except coagulation and kidney function ([not unless clinically indicated in <18 years old])).
- Blood for PCR.
- Urine for PCR.
- Urinalysis (not unless clinically indicated in <18 years old).
- Adverse events.
- Concomitant medications.

9.3.7.2 *Follow-up Week 1, 2, 4, 12, 24 and 48 Clinical and Laboratory/Diagnostic Measurements*

- Vital signs.
- Physical examination (Week 48 only).
- Ophthalmological examination:
 - BCVA,
 - Contrast sensitivity (Weeks 12, 24, 36 and 48 only),
 - Slit-lamp examination,
 - Intraocular pressure (IOP),
 - Fundoscopy,
 - Autofluorescence (Weeks 4, 12, 24 and 48 only),
 - OCT including an infra-red imaging montage,
 - SKP, full-field GATE static perimetry and Microperimetry (Weeks 2, 4, 12, 24, 36 and 48 only),
 - Fundus photography (Weeks 2, 4, 24, 36 and 48 only),
 - Fundus photomontage (Week 48 only),
 - ERG (Weeks 24 and 48 only),
 - VFQ25 questionnaire (Week 48 only) / CVAQC (when possible, 48 week only).
- Clinical Laboratory Samples (except coagulation, at Weeks 4, 24 and 48 only, not in <18 years old unless clinically indicated).
- Urinalysis (Weeks 4, 24 and 48 only), (not unless clinically indicated in <18 years old).
- Pregnancy test (Weeks 4, 12, 24, 36 and 48 only), (not unless clinically indicated in <18 years old).
- Blood for PCR.
- Urine for PCR.
- Blood for Immunology (For all the patients at Weeks 4, 12, and 24 only). In patients with positive antibody response at Week 24, additional immunology blood testing will be performed at Week 36 and/or Week 48 to document the antibody response kinetic until the value returns to baseline in these patients (the need for sample collection beyond Week 48 (if needed) would be collected in the long term safety study).
- Adverse events.
- Concomitant medications.

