4.1 Inclusion Criteria

4.1.1 Main Inclusion Criteria

Patients must meet ALL of the following criteria to be considered for enrolment into this study.

1. Signed and dated written informed consent must be obtained from the patient (or assent in the case of minors from their legal guardian/representative), in accordance with the local regulations.
2. Clinical and molecular diagnosis of RP associated with Usher syndrome type 1B, caused by at least one pathogenic *MYO7A* mutation on both alleles, confirmed by direct sequencing and co-segregation analysis within the patient's family.

3. Patients must have suitable verbal/auditory and/or tactile sign language communication (in the opinion of the investigator) as to allow written informed consent to be obtained.
4. Females of childbearing potential must have a negative urine pregnancy test at screening and at baseline, and agree to use an effective form of contraception such as the contraceptive pill or intra uterine device for at least three months following UshStat administration, or be surgically sterile or postmenopausal, with the last menstrual period being over two years prior to enrollment.
5. Males of reproductive potential must agree with their partner to use two forms of contraception, including one barrier method for at least three months following UshStat administration if their partner is of childbearing capacity, or must be surgically sterile.

Partners of study patients should use barrier contraception for at least three months after UshStat administration.

4.1.2 Specific Inclusion Criteria for Cohorts 1, 2 and 3

- ≥ 18 years of age;
- Concentric constriction of kinetic visual field centrally in the worse seeing eye equating to a horizontal visual field diameter of ≤ 20 degrees, measured through the center of the visual field grid. The visual field constriction will be measured by Semi-automated Kinetic Perimetry (SKP) and the degrees of constriction will be confirmed by centralized independent assessment of the SKP data;
- No detectable rod-derived amplitudes on the full field electroretinogram performed to ISCEV standards.

4.1.3 Specific Inclusion Criteria for Cohort 4

- ≥ 18 years of age;

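### The under-18 exemption from both pre-dose pregnancy tests conflicts with entry criterion 4, and the same schedule footnote makes optional a pre-dose antibody sample that three sections include for children

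*Protocol*

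**What the plan says.** **Eligibility.** Protocol Section 8.2 opens its main inclusion criteria with "Patients must meet ALL of the following criteria to be considered for enrolment into this study". Criterion 4 then reads "Females of childbearing potential must have a negative pregnancy test at screening and at baseline". The Synopsis and SAP Section 4.1.1 repeat it; the SAP wording is "Females of childbearing potential must have a negative urine pregnancy test at screening and at baseline". None of the three sets an age limit.

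**Visit lists.** The screening list in Section 9.3.3 has "Pregnancy test (not unless clinically indicated in <18 years old". Section 9.3.4 makes the Day -1 test an exception to the visit window, "with the exception of the urine pregnancy test that must be negative on Day -1 (not unless clinically indicated in <18 years old", and repeats the exemption in its own list. Section 9.4 gives it again. Section 9.3.7.2 extends it to follow-up: "Pregnancy test (Weeks 4, 12, 24, 36 and 48 only), (not unless clinically indicated in <18 years old".

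**Schedule.** Footnote o, worded identically in Sections 2.1 and 2.2, says: "In subjects of <18 years only investigations may be omitted unless considered clinically indicated". In Section 2.2, which covers Cohort 5, it marks both the screening and the Day -1 pregnancy tests. The Day -1 cell also carries footnote l, which calls for a negative result on Day -1 and mentions no age.

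**Antibody sample.** Footnote o also marks the only pre-dose entry for immunology blood, but not the Week 4, 12 and 24 entries. Section 9.2.8 says that in children "biodistribution and immunology samples will be collected at the same intervals as in adult patients". Section 9.3.4 lists the Day -1 immunology sample with no exemption, directly below three lines that have one. Section 9.3.9 states that the Day -1 sample is required.

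**The concern.** The eligibility rule depends on childbearing potential; the exemption depends on age. Cohort 5 takes patients aged 6-17, so one patient can fall under both. For her, criterion 4 requires two negative tests before dosing, while the schedule and visit lists ask for neither unless someone judges it clinically indicated, a term these passages do not define for this test. Staff preparing a visit work largely from the schedule and visit lists, and the dose cannot be removed once given (Section 8.3).

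The antibody issue is separate and smaller. SAP Table 5A has a Baseline column, and Section 9.3.7.2 continues sampling in antibody-positive patients until the value is back at baseline. Both need a pre-dose value, which footnote o allows a site not to collect in a child.

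**Working it through.** No statistical figure is involved. The check sets each rule beside the text that conflicts with it.

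| Item | Included with no age limit | Omission allowed under 18 |
|---|---|---|
| Pregnancy test, screening | Criterion 4 (Synopsis; Section 8.2; SAP 4.1.1) | Section 9.3.3; footnote o |
| Pregnancy test, Day -1 | Criterion 4; footnote l | Section 9.3.4 (twice); Section 9.4; footnote o |
| Pregnancy test, Weeks 4 to 48 | No passage found that requires it under 18 | Section 9.3.7.2; footnote o |
| Antibody sample, pre-dose | Sections 9.2.8, 9.3.4 and 9.3.9 | Footnote o |

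1. *Pregnancy tests in the visit text.* Screening (1), Day -1 (1) and Weeks 4, 12, 24, 36 and 48 (5) make 7, and all 7 carry the exemption. Criterion 4 covers only the first two, so the contradiction concerns 2 of 2 pre-dose tests and none of the 5 follow-up tests.
2. *Pregnancy tests in the Section 2.2 schedule.* Both pre-dose cells carry footnote o. The Day -1 cell carries o and l together, so one cell both permits omission and demands a negative result. The Week 12 cell shows an undefined mark in the extracted text, possibly a misreading. It does not matter here, because Week 12 is outside the contradiction.
3. *Antibody sample.* The 1 pre-dose entry carries footnote o, against three sections that include the sample. In the extracted tables the mark falls under Day 0 instead of Day -1. This may be extraction damage, but footnote o is on the entry in both schedules.
4. *Who is affected.* All other cohorts are aged 18 or over, so the effect is confined to Cohort 5, up to 6 patients. The number of childbearing potential is not given; the possible range is 0 to 6.

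**The case against.** **Criterion 4 still binds.** All criteria must be met, exclusion 15 bars pregnant women, and Section 9.2.2 has eligibility confirmed before surgery. The exemption permits omission and does not direct it. A site could satisfy every passage by treating childbearing potential as the clinical indication. This stands. A reader might infer that the protocol authorises dosing an adolescent with pregnancy not excluded; it does not, because such dosing would breach criterion 4. What remains is that the operational text does not ask for the evidence the criterion needs.

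**Section 9.2.8 may leave the list of optional tests to the schedule.** It discusses routine bloods, chest X-ray and ECG, then points elsewhere for the investigations that are not compulsory in children. The section number given is 3, the study diagram, which looks like an outdated reference to the schedule. So its silence on pregnancy testing does not show the exemption to be unintended. This stands, but leaves the conflict with criterion 4 untouched.

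**Follow-up tests.** A reader might infer that the exemption in Section 9.3.7.2 is also an error. No passage requires those tests under 18, and reporting a pregnancy as an event of special interest does not depend on a scheduled test. Changing that section would be a preference.

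**Antibody endpoint.** A reader might infer that antibody response could not be judged in children without the pre-dose sample. Protocol Section 13.4.4 and SAP Section 7.5.1 count patients with a response, SAP Table 5A also records positive or negative ELISA and Western blot results, and no passage defines response as a change from baseline. Interpretation would be weaker; loss of the endpoint is not shown. Most of the text already includes the sample, so a missing baseline in every child would require sites to follow the footnote over Sections 9.3.4 and 9.3.9.

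**Conclusion.** Wrong as written, on two separate points.

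- **Pregnancy test.** Criterion 4 and footnote l conflict with the pre-dose exemption in Sections 9.3.3, 9.3.4 and 9.4 and footnote o. A site relying on the schedule and visit lists could dose a Cohort 5 patient without either of the two tests criterion 4 requires. The ceiling is 6 patients. The actual number may be zero, since Cohort 5 is optional and the number of childbearing potential is unknown.
- **Antibody sample.** One schedule footnote conflicts with three sections. If the sample were omitted, that child would have no entry for the Baseline column of SAP Table 5A and no reference for the return-to-baseline rule.

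Both conclusions assume that Part C opens under this text and that some sites follow the schedule. Nothing suggests that harm occurred: the adverse event table shell in the 2019 memorandum attached to the SAP shows only Cohorts 1 to 3, with 9 patients.

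**What to change.** Before Part C opens:

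1. Reconcile the pre-dose pregnancy-test exemption in footnote o and Sections 9.3.3, 9.3.4 and 9.4 with criterion 4 and footnote l, so that schedule and eligibility rule define the same tested group. Which clinical rule should prevail is for the sponsor and investigators to settle. If criterion 4 itself changes, the Synopsis and SAP Section 4.1.1 must follow.
2. Correct footnote o on the pre-dose immunology entry so that it agrees with Sections 9.2.8, 9.3.4 and 9.3.9.

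Section 9.3.7.2 needs no change on this ground.

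The cost is wording in a protocol amendment. If reconciliation leads to testing some adolescents, Section 9.3.14 already allows a urine dipstick at the site. The antibody correction adds no procedure beyond the blood sample that Sections 9.3.4 and 9.3.9 already call for.

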9.3.5 Re-screening

Re-screening will be allowed once within 90 day period from initial informed consent, in case patient was eligible by all inclusion – exclusion criteria, but was not treated. All eligibility criteria need to be reviewed. Patient will undergo a baseline visit (if was not done) or repeat it within a 7 days period before surgery.

Additional (standard) examinations/ tests can be needed during such visit:

- Laboratory tests of hematology, chemistry panel, kidney function, liver function and coagulation will be repeated if done earlier than 38 days before surgery, or – by a request of anesthesiologist.
- Anesthesia assessment and physical examination will be repeated if outside of the Day -28 to Day -1 window before surgery. Weight, ECG, chest X-ray and additional physical examination may be repeated by a request of anesthesiologist.

